11.2 Use of rescue therapy

The use of rescue therapy will be identified as a ‘yes’ response to the “Rescue Medication?” question on the Prior and Concomitant Medications CRF, or plasma exchange as collected on concomitant medical procedure CRF”.

The number and percentage of study participants who used of rescue therapy by study cycle and the actual dose received in that cycle will be summarized using SS.

Data from study participants who used rescue therapy will be listed using the FAS.

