Eligible study participants from MG0004 who have completed at least 6 scheduled visits in the Treatment Period and the premature end of treatment (PEOT) visit can move directly into the Observation Period in MG0007 of the initial fixed cycle. Additionally, eligible study participants from MG0004 who are in the Observation Period and have completed the EOS visit can move directly into the Observation Period in MG0007 of the initial fixed cycle (Figure 1-1 and Figure 1-2). If IMP treatment was withheld for low IgG in MG0004, study participant's missed dose(s) can be counted as part of the total 6 visits for completion of MG0004 and meet eligibility

requirements for MG0007. These study participants will undergo their first MG0007 treatment with rozanolixizumab upon worsening of gMG symptoms. For the first MG0007 treatment with rozanolixizumab, participants will continue on their last treatment dose from MG0004. Dose adjustments may be applied in future cycles as per description below.

The rollover into MG0007 must be completed within 4 weeks after the End of Study (EOS) visit from MG0003, or the PEOT or EOS (as appropriate) visit from MG0004. In the event a study participant has a gap period (>4 weeks) between the EOS or PEOT visit from the lead-in study and the start of MG0007, a Screening Period (see Appendix 11 [Section 10.11]) of up to 4 weeks will be applicable to confirm that the study participant still meets the eligibility criteria for entry into MG0007 (see Appendix 12 [Section 10.12]).

Figure 1-1: MG0007 entry schema

MG=myasthenia gravis

In case of symptom worsening (eg, an increase of 2.0 points on the MG-ADL or 3.0 points on the QMG scale) between assessments, resulting in a need for additional treatment, study participants will undergo another 6-week treatment cycle followed by an Observation Period, based on the Investigator's discretion. The dose may be adjusted to 7mg/kg or 10mg/kg at the beginning of each treatment cycle based on the Investigator's discretion. The minimal time to start the next treatment cycle is 4 weeks following the last dose of the Treatment Period of the previous cycle. If a study participant requires treatment earlier than 4 weeks, IgG levels from the previous cycle should be considered and discussed with the Medical Monitor. A new treatment cycle **should not** be initiated until total IgG level is $\geq 2\text{g/L}$.

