3.2.2 Study periods

The study cycle consists of the following:

- Treatment Period: 6 weeks
- Observation Period: 16 weeks
- Non-treatment period

The following definitions for starting and entering the study periods for each cycle will be applied:

- **Treatment Period** starts with the first day of IMP in each cycle in MG0007 and ends after Day 43 or PEOT assessments. All participants in the Safety Set will be considered to have started the Treatment Period. A participant is considered to have completed the Treatment Period of each cycle if assessments from Treatment Period Day 43 are completed.
- **Observation Period** starts with one day after the end of the Treatment Period of each cycle and ends after the final assessments at Day 155 visit. Participants with assessment on any Observation Period day are considered to have started the Observation Period.
- **Non-treatment period** starts with one day after the end of the Observation Period of each cycle and ends before the start of next cycle or the EOS assessment.

A study participant is considered to have completed the study if he/she has completed all phases of the study including the Observation Period and the EOS visit assessments. The end of the study is defined as the date of the last visit of the last participant in the study.

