3.9 Changes to protocol-defined analyses

In the protocol section 9.2.1, the intercurrent events to be considered are the use of rescue therapy prior to Day 43 and permanent treatment discontinuation (or withdrawal from study) due to TEAEs. In the SAP, we consider use of rescue therapy prior to Day 43 and permanent treatment discontinuation due to TEAEs as intercurrent events.

In the protocol, the treatment policy strategy is described for the analysis meaning that all data was planned to be analyzed regardless of study participants receiving treatment with rescue therapy. Summaries will also be presented for the efficacy endpoints where participants will be censored at the time that they take rescue medication. In the SAP, time to MG-ADL response will be analyzed censoring the data at the time of the use of rescue therapy and all other efficacy endpoints will be summarized following treatment policy.

Protocol amendment 3 did not mention how to treat IgG when participants receive rescue therapy. In the SAP, the IgG values up to and including 8 weeks after start date of rescue therapy will be excluded from the analysis.

In the protocol section 8.3.1, Hy's law is defined as $>3 \times \text{ULN}$ ALT or AST with coexisting $>2 \times \text{ULN}$ total bilirubin in the absence of $<2 \times \text{ULN}$ ALP, with no alternative explanation for the biochemical abnormality (ie, without waiting for any additional etiologic investigations to have been concluded). In this SAP, Hy's law is defined as (AST or ALT $\geq 3 \times \text{ULN}$) and TBL $\geq 2 \times \text{ULN}$ and ALP $< 2 \times \text{ULN}$ to be consistent with Rozanolixizumab program SAP.

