9.11 Time between consecutive treatment cycles

The time between treatment cycles is calculated as: date of first sc infusion in consecutive cycle - date of last sc infusion before new cycle + 1 (or date of censoring - date of last sc infusion before potential new cycle + 1).

Discontinued participants will be censored at their discontinuation date and completers will be censored at their last visit date.

The number and percentage of study participants with ≤ 21 , $21 <= 28$, $28 <= 60$, $60 <= 90$, $90 <= 120$, $120 <= 150$, $150 <= 180$, $180 <= 300$, $300 <= 400$, $400 <= 500$, ..., $900 <= 1000$ days between study cycles will be summarized by treatment group in the proceeding cycle and RLZ total. Mean, SD, median, min and max will also be calculated for time between consecutive treatment cycles by treatment groups in the proceeding cycle and RLZ total. The same summaries will be repeated but participants who had no event in a specific cycle will be excluded from that cycle analysis.

Survival estimates for day 1, 28, 60, 90, 120, 150, 180, 300, 400, 500, 600, 700, 800, 900 and 1000 will be calculated using Kaplan-Meier method by treatment group in proceeding cycle and

RLZ total. The median times (with 95% CI) between study cycles and cumulative number of events by study cycle will also be reported. The survival event is defined as the start of subsequent cycle since last sc infusion of preceding cycle. Number of censored participants will be reported as well.

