11.3 Time to first rescue therapy

Time to first rescue therapy (in days) is defined as: Date of first post-baseline rescue therapy use - Date of first IMP in the study + 1.

For participants who do not take rescue therapy, discontinued participants will be censored at their discontinuation date and completers will be censored at their last visit date.

The survival estimates of 1, 29, 43, 71, 99, 127, 155, 180, 300, 400, 500, 600, 700, 800, 900, and 1000 days to rescue therapy and the median times (with 95% CI) to rescue therapy will be

calculated using Kaplan-Meier method by initial RLZ dose level and RLZ total. Number of censored participants will be reported as well.

The median times to rescue therapy by study cycle will be calculated using Kaplan-Meier method for RLZ dose level received within study cycle and RLZ total. 95% CI of median times will be reported as well.

The time to rescue therapy will be listed using FAS.

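### SAP 11.2 gives one crude rescue percentage per open-ended study cycle, so by-cycle and by-dose figures are not comparable, and from cycle 2 onward no table counts rescue before Day 43

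*SAP*

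**What the plan says.** SAP 11.2 plans a count with its percentage: "participants who used of rescue therapy by study cycle and the actual dose received in that cycle will be summarized using SS". It sets no time limit, no split by period and no adjustment for time at risk.

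SAP 3.2.2 builds a study cycle from the 6-week Treatment Period, the 16-week Observation Period and a non-treatment period that "ends before the start of next cycle or the EOS assessment".

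Protocol 6.5.4 and 7.1.4 treat rescue differently by timing. Rescue in the Treatment Period rules out further rozanolixizumab. After rescue in the observation or no-treatment periods, the participant may stay in the study.

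SAP 3.9 says: "In the SAP, we consider use of rescue therapy prior to Day 43 and permanent treatment discontinuation due to TEAEs as intercurrent events". It keeps censoring at rescue only for time to MG-ADL response; every other efficacy endpoint follows treatment policy. The secondary change-from-Baseline endpoints are read at Day 43 in each of the first three cycles (SAP 2.2.2.1).

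SAP 11.3 adds Kaplan-Meier estimates of time to first rescue at fixed days, including Day 43. These are counted from the first IMP in the study and grouped by initial dose. By cycle it says only: "The median times to rescue therapy by study cycle will be calculated using Kaplan-Meier method", with a 95% CI.

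**The concern.** A crude percentage is a fair summary when everyone is followed for about the same time. Here the window closes when the participant starts the next cycle or leaves the study, so its length depends partly on how long the effect lasts and partly on when the study ends. A dose or cycle can show more rescue because its participants were watched for longer, and a late cycle cut short by EOS can show less.

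The single figure also hides which kind of rescue occurred, although the protocol attaches different consequences to each.

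Finally, under treatment policy a reader needs to know how many Day 43 scores in each cycle follow rescue. For cycles 2 and 3 no planned table supplies that count.

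**Working it through.** The plan states no rescue rate, so there is no figure to reproduce. The rates below are assumptions.

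**Window length.** Protocol Table 1-3 puts the last scheduled dose at Day 36. On the next cycle, Protocol 1.1 says: "The minimal time to start the next treatment cycle is 4 weeks following the last dose". Adding 28 days puts the next first dose at Day 64, a cycle of about 63 days. Earlier starts are possible after discussion with the Medical Monitor, so 63 days is the usual minimum and not a floor. There is no upper limit.

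**Constant rate.** P(rescue in cycle) = 1 − exp(−rate × days / 365.25).

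| Assumed rate per participant-year | 100-day cycle | 200-day cycle |
|---|---|---|
| 0.05 | 1.4% | 2.7% |
| 0.10 | 2.7% | 5.3% |
| 0.20 | 5.3% | 10.4% |

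For the middle row: 1 − exp(−0.10 × 100/365.25) = 2.7% and 1 − exp(−0.10 × 200/365.25) = 5.3%. The rate is the same, yet the percentage nearly doubles.

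**Does the direction hold if a longer effect also lowers the rescue risk?** Let L be the days from last dose to next cycle. The cycle then has 42 days up to Day 43 and L − 7 days after it. Assume a risk of 1% per 28 days, and let the hazard after Day 43 be multiplied by (28/L)^k.

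| k | L = 28 | L = 60 | L = 120 |
|---|---|---|---|
| 0 (constant) | 2.24% | 3.35% | 5.41% |
| 1 (falls in proportion) | 2.24% | 2.37% | 2.42% |
| 1.5 (falls faster) | 2.24% | 2.09% | 1.95% |

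The percentage can rise, stay nearly flat or fall. Against L = 28, the hazard ratio after Day 43 that leaves the percentage unchanged is 21/53 = 0.40 at L = 60 and 21/113 = 0.19 at L = 120.

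**Pooling.** Take two hypothetical doses with the same assumed 1% per 28 days after Day 43, so the daily hazard is −ln(0.99)/28.

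- Dose A, 4% rescued by Day 43, L = 60: 1 − 0.96 × exp(−hazard × 53) = 5.8%.
- Dose B, 2% rescued by Day 43, L = 120: 1 − 0.98 × exp(−hazard × 113) = 5.9%.

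A twofold difference in on-treatment rescue disappears from the per-cycle figure.

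**Rescue before Day 43, by cycle.**

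- Cycle 1: the Kaplan-Meier estimate at Day 43 in SAP 11.3 starts at the first IMP in MG0007, which is Day 1 of cycle 1. It gives this figure by initial dose.
- Cycle 2 onward: SAP 11.3 gives a median only. It is not reached while the estimated cumulative proportion rescued stays below one half, and it says nothing about Day 43. The only time origin defined is the first IMP in the study, so none is stated for a by-cycle analysis.
- SAP 6.4 summarizes rescue medications without stating a split by cycle or period.

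**The case against.** A reader might infer that a longer-lasting effect must produce a higher rescue percentage. The documents do not support that. Rescue is for participants who still have moderate to severe symptoms, so a longer effect may well lower the risk between cycles, and the table above shows the direction can reverse.

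A reader might also take the longest landmark in SAP 9.11 ("Survival estimates for day 1, 28, 60, 90, 120, 150, 180, 300, 400, 500, 600, 700, 800, 900 and 1000") as the length cycles will reach. It is a reporting grid of days, much the same as those in SAP 9.6 and 11.3, and says nothing about expected cycle lengths.

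It would equally be wrong to say that rescue before Day 43 is missing for every cycle, because SAP 11.3 covers cycle 1.

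Three further points count against giving this much weight:

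- Rescue use (yes/no) is an 'other' endpoint and all analyses are descriptive.
- Rescue users and times to rescue are listed, and SAP 6.4.2 assigns medications to periods, so a patient reader could reconstruct the counts.
- SAP 6.4.1 ties concomitant medications to the Treatment and/or Observation Period. That could be read as closing the window at Day 155, although SAP 11.2 states no such limit.

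These lower the importance but do not remove the problem. A listing is not a table. Even a window closed at Day 155 would range from about 63 to 155 days, or 1.7% to 4.2% at 0.10 per participant-year.

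**Conclusion.** The point stands in limited form. The per-cycle, per-dose percentage in SAP 11.2 covers unequal time at risk and pools two kinds of rescue, so its values are not comparable between cycles or doses. That follows from the definitions alone.

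The size does not. The change from 2.7% to 5.3% rests on an assumed constant 0.10 per participant-year and an assumed doubling of cycle length. A longer interval raises the percentage only if the off-treatment hazard does not fall in proportion. The missing count of rescue before Day 43 concerns cycle 2 onward only, and matters most for cycles 2 and 3, where Day 43 endpoints are read under treatment policy. Priority is low to moderate.

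**What to change.** In SAP 11.2, split the table by cycle and dose received into two windows:

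- (a) First dose of the cycle to Day 43/PEOT, as number and percentage, with everyone who started the cycle as denominator. A footnote should say which boundary applies when PEOT comes before Day 43, because SAP 3.2.2 ends the Treatment Period at PEOT while SAP 3.9 counts to Day 43.
- (b) After that until the next cycle or EOS, as number and percentage plus events per participant-year in that window, using the 365.25-day year of SAP 8.1. By-cycle Kaplan-Meier estimates at fixed days, counted from the first IMP of that cycle, would serve instead of the rate.

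The period assignment in SAP 6.4.2 can be used, but it needs an added rule for the non-treatment period, which it now shows only as NA.

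The cost is that rule, one new person-time derivation and extra table rows. Rescue and dosing dates are already collected. The change does not make later-cycle dose comparisons randomised, because dose can be changed at the Investigator's discretion at the start of each cycle; a footnote should say so.

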11.3 Time to first rescue therapy

Time to first rescue therapy (in days) is defined as: Date of first post-baseline rescue therapy use - Date of first IMP in the study + 1.

For participants who do not take rescue therapy, discontinued participants will be censored at their discontinuation date and completers will be censored at their last visit date.

The survival estimates of 1, 29, 43, 71, 99, 127, 155, 180, 300, 400, 500, 600, 700, 800, 900, and 1000 days to rescue therapy and the median times (with 95% CI) to rescue therapy will be

calculated using Kaplan-Meier method by initial RLZ dose level and RLZ total. Number of censored participants will be reported as well.

The median times to rescue therapy by study cycle will be calculated using Kaplan-Meier method for RLZ dose level received within study cycle and RLZ total. 95% CI of median times will be reported as well.

The time to rescue therapy will be listed using FAS.

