The rollover into MG0007 must be completed within 4 weeks after the EOS visit from MG0003, or the PEOT or EOS (as appropriate) visit from MG0004. In the event a study participant has a gap period (>4 weeks) between the EOS or PEOT visit from the lead-in study and the start of MG0007, a Screening Period of up to 4 weeks will be applicable to confirm that the study participant still meets the eligibility criteria for entry into MG0007.

Figure 2-1: MG0007 entry schema

[figure not shown]
In case of symptom worsening (eg, an increase of 2.0 points on the MG-ADL or 3.0 points on the QMG scale) between assessments, resulting in a need for additional treatment, study participants will undergo another 6-week treatment cycle followed by an Observation Period, based on the Investigator's discretion. The dose may be adjusted to 7mg/kg or 10mg/kg at the beginning of each treatment cycle based on the Investigator's discretion. The minimal time to start the next treatment cycle is 4 weeks following the last dose of the treatment period of the previous cycle. If a study participant requires treatment earlier than 4 weeks, IgG levels from the previous cycle should be considered and discussed with the Medical Monitor. A new treatment cycle **should not** be initiated until total IgG level is $\geq 2\text{g/L}$.

Participants in MG0007 will remain on their gMG background medications. With the exception of corticosteroids and acetylcholinesterase (AChE) inhibitors, all gMG medication doses should be maintained during each respective 6-week treatment cycle and efforts should be made to maintain a stable dose during the first 8 weeks of the Observation Period.

Study participants who receive rescue therapy (intravenous immunoglobulin [IVIg], plasma exchange [PEX], subcutaneous immunoglobulin [SCIg], or iv corticosteroid) during the Treatment Period are not eligible to receive any further treatment with rozanolixizumab. These participants must complete the first 8 weeks of the Observation Period after the last dose of rozanolixizumab prior to completing the EOS visit assessments, and subsequently will be withdrawn from the study.

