2.3.2 Dosing

This OLE study will continue treatment with rozanolixizumab subcutaneous (sc) fixed doses across body weight tiers equivalent to approximately 7mg/kg and 10mg/kg administered QW for 6-week treatment cycle (Table 2–1). Weight-based dose adjustments should be limited to a maximum of every 6 months during the study.

If one of the doses described in Table 2–1 is determined to be futile and is discontinued in MG0003, then that dose arm will be dropped from MG0007, and study participants in the affected dose arm will be transferred to an adjusted dose.

Dose modifications from 10mg/kg to 7mg/kg equivalent and vice versa are permitted at the beginning of the treatment cycles at the Investigator's discretion, and if the benefit-risk remains favorable for the study participant. Recommended dose modifications from 10mg/kg to 7mg/kg equivalent due to drug-related adverse events may include but are not limited to:

- Moderate to severe headaches that are considered to be related to rozanolixizumab
- Moderate to severe gastrointestinal (GI) disturbances that are considered to be related to rozanolixizumab
- Moderate to severe toxicities (\geq Grade 2 as defined by Common Terminology Criteria for Adverse Events [CTCAE], version 5.0) for which rozanolixizumab cannot be excluded as a cause
- Recurrent hypogammaglobulinemia with a serum total IgG level of <2 g/L.

Table 2–1: MG0007 dose levels and weight tiers

Bodyweight	Rozanolixizumab dose equivalent	
	7mg/kg Dose 1	10mg/kg Dose 2
≥35 to <50kg	280mg	420mg
≥50 to <70kg	420mg	560mg
≥70 to <100kg	560mg	840mg
≥100kg	840mg	1120mg

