3.3 Definition of Baseline values

For the analyses done by entire study, Baseline values will be the last available value prior to or on the same date of first administration of IMP in MG0007. Scheduled or unscheduled measurements can be used as the Baseline value.

For the analyses done by study cycle, Baseline values will be defined as the last available value prior to or on the same date (and same time if time is collected for the individual assessment) of first administration of IMP at each cycle (ie Baseline [Day 1]) value for that cycle.

In case of baseline of specific cycle is missing, values from previous cycle or previous studies EOS visit will be considered as baseline for that cycle.

For [REDACTED] Baseline values will be the Baseline values determined in MG0003.

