9.6 Time to first MG-ADL response

Time to First MG-ADL response (in days) by study cycle is defined as Date of First post-Baseline MG-ADL Response (≥ 2.0 points improvement from Baseline) within study cycle - Date of first IMP within study cycle + 1. Participants will be excluded from the survival analysis for a cycle if they did not have IMP in that cycle.

Study participants who use rescue therapy within study cycle before achieving first MG-ADL response within study cycle will be censored at time of rescue intake. For non-responders who take rescue therapy, they will be censored at the date taken rescue therapy, or last non-missing post Baseline MG-ADL visit, whichever is earlier. For non-responders who do not take rescue therapy, they will be censored at the last non-missing post-Baseline MG-ADL visit date.

The survival estimates of 1, 8, 15, 22, 29, 36, 43, 71, 99, 127, 155, 180, 300, 400, 500, 600, 700, 800, 900 and 1000 days to first MG-ADL response, median times to MG-ADL response with 95% CI, and cumulative number of events by study cycle will be calculated using Kaplan-Meier method for RLZ dose level received within study cycle and RLZ total. Number of censored study participants will be reported as well. A Kaplan-Meier plot will also be generated by study cycle and treatment group.

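### SAP 11.3 asks for time to rescue by cycle but defines it only from the first dose in the study, so medians for cycle 2 onward would include time from earlier cycles

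*SAP*

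**What the plan says.** SAP 11.3 (Time to first rescue therapy) defines the variable once: "Date of first post-baseline rescue therapy use - Date of first IMP in the study + 1". For participants without rescue, "discontinued participants will be censored at their discontinuation date and completers will be censored at their last visit date". Fixed-day survival estimates up to day 1000, and medians, are then requested by initial dose level and in total.

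The section goes on: "The median times to rescue therapy by study cycle will be calculated using Kaplan-Meier method for RLZ dose level received within study cycle". It asks for 95% confidence intervals for these medians. It gives no second start date, no censoring at the end of a cycle, no delayed-entry rule, and no rule for a participant whose first rescue came before the cycle in question.

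Other time-to-event sections of the SAP set their own clocks. Section 9.6 (time to first MG-ADL response) subtracts "Date of first IMP within study cycle + 1" and leaves out participants not dosed in the cycle. Section 9.11 (time between cycles) counts from "date of last sc infusion before new cycle + 1".

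**The concern.** A clock that starts at the first dose in the study suits an analysis of the whole study by initial dose. It does not suit a median reported for cycle 2, 3 or 4. A participant must already have passed through the earlier cycles to be in those groups, and the written rule adds that elapsed time to the time to rescue.

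The study is about repeated cycles. A table in which median time to rescue lengthens from one cycle to the next would naturally be read as sustained or growing benefit. Under this rule it would lengthen even if the within-cycle risk of rescue never changed.

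Two further gaps follow from the same definition. It counts only the first rescue in the study, although SAP 2.3.1 allows some participants to continue after a rescue outside the Treatment Period. And censoring at discontinuation or last visit in the study lets follow-up for any cycle, including the first, run past the start of the next one.

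**Working it through.** The plan states no figure to reproduce here. The check is date arithmetic from the schedule, followed by an illustration.

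**Inputs**
- Dosing: "administered QW for 6-week treatment cycle" (SAP 2.3.2). The schedules of activities in the protocol (Tables 1-2 and 1-3) place the six doses on Days 1, 8, 15, 22, 29 and 36, with a window of ±2 days on the last.
- Interval: "The minimal time to start the next treatment cycle is 4 weeks following the last dose of the treatment period of the previous cycle" (SAP 2.3.1). The same section contemplates an earlier start after discussion with the Medical Monitor.
- Cycle length: 6 weeks of treatment plus 16 weeks of observation (SAP 3.2.2), with a possible non-treatment period afterwards.

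**Extra time carried per earlier cycle**
1. Last dose: Day 1 + 5 × 7 = Day 36.
2. Next cycle at the standard interval: Day 36 + 28 = Day 64, an offset of 64 − 1 = 63 days.
3. With the last dose on Day 34 or Day 38, the offset is 61 or 65 days.
4. Full cycle: 22 × 7 = 154 days. It is longer if a non-treatment period follows.

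| Cycle | Offset at standard interval, full dosing | Offset if earlier cycles run 22 weeks | Rescue on cycle Day 29 is recorded as |
|---|---|---|---|
| 1 | 0 | 0 | Day 29 |
| 2 | 63 | 154 | Day 92 to 183 |
| 3 | 126 | 308 | Day 155 to 337 |
| 4 | 189 | 462 | Day 218 to 491 |

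**Illustration of the effect on a median.** The assumptions are not from the documents: constant rescue hazard, identical in every cycle; cycle lengths uniform over 63 to 154 days; 200,000 simulated participants per scenario. Follow-up was cut at the end of each cycle under both clocks, and everyone entered every cycle, so the comparison isolates the start date alone.

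| True within-cycle median | Clock from first dose of cycle, cycles 1 to 4 | Clock from first dose of study, cycles 1 to 4 |
|---|---|---|
| 60 | 60, 61, 60, 61 | 60, 173, 285, 397 |
| 90 | 90, 90, 90, 90 | 90, 202, 313, 425 |
| 120 | 120, 121, 121, 120 | 120, 231, 343, 454 |

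Under these assumptions the reported median grows by about 112 days per cycle when nothing has changed.

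**Does another section supply the missing start date?** SAP 3.3 says that, for analyses by cycle, "Baseline values will be defined as the last available value prior to or on the same date" as that cycle's first dose. This resets Baseline values, not the start date in 11.3. SAP 3.2.1.1 takes the first MG0007 infusion as its reference for relative day, which agrees with the study-level clock. Sections 9.6 and 9.11 state their own clocks, so no general by-cycle convention can be assumed for 11.3.

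**The case against.** The best defence is that the study-level definition was meant for the entire-study analysis that follows it, and that a cycle-level start was intended for the separate by-cycle sentence. That sentence drops the word first and refers to dose received within the cycle. SAP 3.3 ties by-cycle Baseline to each cycle's first dose, and SAP 11.2 already assigns rescue use to cycles. This may well be what the authors meant, but it is not written, and a programmer has only one definition to apply. Reading post-baseline in the definition as cycle Baseline would let a later-cycle rescue count, but the date subtracted would still be the first dose in the study.

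The defence is stronger on impact. Time to rescue sits under the other objectives, and all analyses are descriptive (SAP 4.6). SAP 11.2 reports the number and percentage using rescue by cycle and dose, so later-cycle rescue is not hidden. No rescue rate is given, and if rescue is rare the medians may not be reached under either clock. SAP 9.6, useful as a model for the start date, does not censor at the next cycle either. All of this stands and limits the weight of the point.

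Four stronger readings are tempting, and the documents do not support them:
- That 63 and 126 days are minimum offsets. Visit windows, earlier starts and truncated dosing can all give less.
- That every cycle 2 or later time contains the whole of the earlier cycles. On the literal rule, a participant rescued in an earlier cycle keeps that earlier date.
- That the by-cycle tables must show zero rescue by day 43 after cycle 1. Fixed-day estimates are planned only by initial dose and in total; by cycle, only medians are planned.
- That the dose comparison in later cycles is biased. A similar offset in both dose groups would largely cancel in a difference of medians. Bias between doses needs earlier-cycle lengths to differ by dose, which nothing in the documents shows.

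**Conclusion.** The point holds in a limited form. The only rule SAP 11.3 states gives a wrong result when used for the by-cycle medians it requests. It adds earlier-cycle time, ignores a later-cycle rescue in someone already rescued in an earlier Observation Period, and lets follow-up run past the next cycle's start.

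The added time is about 63 days per earlier cycle, assuming six doses and the standard 4-week interval, and 154 days if each earlier cycle runs its full 22 weeks. It is less with early starts or truncated dosing. The simulated medians show direction and scale only, because they rest on assumed hazards and cycle lengths.

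The start date for cycle 1, the entire-study analysis by initial dose, and the rescue counts in SAP 11.2 are not affected. The text should be corrected, but no primary or secondary conclusion depends on it.

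**What to change.** Keep the present definition for the entire-study analysis. Add a by-cycle definition to SAP 11.3: date of first rescue within the study cycle, minus date of first IMP within that cycle, plus 1, for participants dosed in that cycle. Censor at the earliest of first IMP of the next cycle, discontinuation, or last visit.

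By-cycle Kaplan-Meier estimates at fixed days, for example 43, 99 and 155, would be a useful optional addition because the medians may not be reached. They are not needed to correct the error.

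The cost is a short SAP edit and a small programming change. No new data are needed: rescue dates are recorded under protocol 6.5.4, and IMP administration details are already listed under SAP 8.1.
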